### **6.4.3 Prohibited concomitant therapy**

During the course of the study, patients may not receive other additional investigational drugs, agents, devices, chemotherapy, or any other therapies that may be active against cancer. However, limited-field palliative radiotherapy to non-target lesion(s) may be allowed as concomitant therapy after documented discussion with Novartis. For patients with anaplastic thyroid cancer, limited-field radiotherapy to a target lesion that is life-threatening may be allowed, provided that other measurable disease remains to allow an assessment of response to treatment. These cases must be discussed with Novartis with written permission. Such local therapies administered during the study treatment must be listed on the Concomitant Antineoplastic Therapy – Radiotherapy CRF.

After progression of disease as per RECIST criteria, radiotherapy and surgery to select target and non-target lesion(s) (such as brain metastases) may be allowed as concomitant therapy after documented discussion and approval by Novartis.

Additionally, no other therapeutic monoclonal antibodies and no immunosuppressive medication may be administered while on this study.

The use of systemic steroid therapy is not allowed, except for the treatment of the following: infusion reactions, immune-mediated toxicities (patients may resume study treatment while on tapering with doses  $\leq$  10 mg/day prednisone or equivalent), COPD exacerbation and replacement-dose steroids in the setting of adrenal insufficiency. Additional exceptions may be discussed with Novartis. Topical, inhaled, nasal and ophthalmic steroids are not prohibited.

The use of live vaccines is not allowed through the whole duration of the study.

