### **10.4.4 Supportive analyses**

As a supportive analysis of the primary endpoint for Phase II, a Bayesian hierarchical model with a flexible exchangeability design will be applied on ORR including data from all indications. Exchangeability of indication parameters will be assessed; for the Bayesian methodology and an application to binary data see [Thall \(2003\)](#) and [Chugh \(2009\)](#).

Moreover, the primary analysis of the phase II will be repeated using the PPS.

If there is a substantial number of patients receiving palliative radiotherapy, sensitivity analyses of ORR will be performed where the tumor response assessments are censored at the time of palliative radiotherapy. BOR is determined by the best response recorded between the date of first dose of treatment and date of objectively documented progression or date of subsequent anticancer therapy (including on-treatment palliative radiotherapy of non-target or target lesions), whichever occurs first.

Additional supportive [REDACTED] analyses will be conducted to support the primary objective, if appropriate, and the details of these analyses will be defined in the RAP.

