### 14.1.3.1 Best overall response

The best overall response is the best response recorded from the start of the treatment until disease progression/recurrence (taking as reference for PD the smallest measurements recorded since the treatment started). In general, the patient's best response assignment will depend on the achievement of both measurement and confirmation criteria.

The best overall response will usually be determined from response assessments undertaken while on treatment. However, if any assessments occur after treatment withdrawal the protocol should specifically describe if these will be included in the determination of best overall response and/or whether these additional assessments will be required for sensitivity or supportive analyses. As a default, any assessments taken more than 150 days after the last dose of study treatment will not be included in the best overall response derivation. If any alternative cancer therapy is taken while on study any subsequent assessments would ordinarily be excluded from the best overall response determination. If response assessments taken after withdrawal from study treatment and/or alternative therapy are to be included in the main endpoint determination, then this should be described and justified in the protocol.

Where a study requires confirmation of response (PR or CR), changes in tumor measurements must be confirmed by repeat assessments that should be performed not less than 4 weeks after the criteria for response are first met.

Longer intervals may also be appropriate. However, this must be clearly stated in the protocol. The main goal of confirmation of objective response is to avoid overestimating the response rate observed. In cases where confirmation of response is not feasible, it should be made clear when reporting the outcome of such studies that the responses are not confirmed.

- For non-randomized trials where response is the primary endpoint, confirmation is needed.
- For trials intended to support accelerated approval, confirmation is needed
- For all other trials, confirmation of response may be considered optional.

The best overall response for each patient is determined from the sequence of overall (lesion) responses according to the following rules:

- CR = at least two determinations of CR at least 4 weeks apart before progression where confirmation required or one determination of CR prior to progression where confirmation not required

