3.4 Efficacy evaluation

Analysis of efficacy endpoints will be performed using the FAS.

Assessment by irRC

For irRC (see [CPDR001X2101 Amendment 8 Appendix 14.2]) the key difference from RECIST v1.1 (see [CPDR001X2101 Amendment 8 Appendix 14.1]) in the assessment of these endpoints is the recommendation that irPD be confirmed at least 4 weeks after the criteria for irPD are first met. A single assessment of irPD followed by a subsequent assessment of irSD or better will be considered as a pseudo-progression, these are not considered as progression events for the purposes of analysis. Where irPD is confirmed by a second assessment, the date of the first of these two assessments is then the date of progression. For patients who have ended treatment without a valid confirmation assessment, for the purposes of analysis the single assessment of irPD will be treated as a confirmed irPD. At time of analysis there may be patients whose last adequate assessment is an unconfirmed irRC progression but who are continuing treatment. In these cases that progression will be treated as a confirmed progression for the primary analysis, and sensitivity analysis of time to event endpoints may be conducted in which the patient is censored at the time of last adequate assessment. Additional definitions and derivation rules for irRC are provided in Section 4.2.

Best overall response (BOR)

The BOR is the best response recorded from the start of the treatment until disease progression/recurrence. For RECIST v1.1 and irRC, any assessments taken before the start of any further antineoplastic therapy will be considered in the assessment of BOR in recognition that response to immunotherapy may be delayed. For both RECIST v1.1 and irRC, if any alternative antineoplastic therapy is taken while on study, any subsequent assessments will be excluded from the BOR determination.

Per RECIST v1.1, CR and PR need to be confirmed with at least two determinations of CR or PR respectively at least 4 weeks apart before progression. In order to classify overall response as SD, a patient must have at least one SD assessment (or better) > 6 weeks after start date of study treatment. In order to classify overall response as PD, a patient must have progression < 12 weeks after start date of study treatment.

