Per irRC, irCR, irPR and irPD need to be confirmed with at least two determinations of irCR or irPR or irPD, respectively at least 4 weeks apart. In order to classify overall response as irSD, the patient must have at least one SD assessment (or better) > 6 weeks after start date of study treatment.

Individual lesion measurements and overall response assessments will be listed by patient and assessment date. Best overall response (BOR) per RECIST v1.1 and per irRC will be listed and tabulated.

Overall response rate (ORR) and Disease control rate (DCR)

ORR is the proportion of patients with a best overall response of CR or PR (RECIST v1.1) or of irCR or irPR (irRC). DCR is the proportion of patients with a best overall response of CR, PR, or SD (RECIST v1.1) or of irCR, irPR, or irSD (irRC).

Progression free survival (PFS)

For assessment per RECIST v1.1, PFS is the time from date of start of treatment to the date of event defined as the first documented progression or death due to any cause. If a patient has not had an event, PFS is censored at the date of last adequate tumor assessment ([CPDR001X2101 Amendment 8 Appendix 14.1.3.2.1]). For irRC, PFS is defined similarly, but with the date of event defined as the date of the first documented confirmed progression as defined in Section 4.2.3, or death due to any cause. For irRC, other censoring rules are applied as for RECIST v1.1 ([CPDR001X2101 Amendment 8 Appendix 14.1.3.2.9]).

Duration of response (DOR)

DOR applies only to patients with a BOR of confirmed CR or PR (RECIST v1.1) or of confirmed irCR or irPR (irRC). For assessment per RECIST v1.1, DOR is defined as the time from the date of the first documented response (CR or PR) to the date of first documented progression, or death due to any cause. For assessment per irRC, DOR is defined as the time from the first confirmed response (irCR or irPR), to the date of confirmed progression as defined in Section 4.2.3, or death due to any cause.

Use of alternative cancer therapy

For both RECIST v1.1 and irRC, if any alternative cancer therapy is taken other than palliative radiotherapy any subsequent assessments will be excluded from the analysis of endpoints based on tumor response assessments. If a substantial number of patients receive palliative radiotherapy, sensitivity analyses of these endpoints may be performed where assessments are also censored at the time of palliative radiotherapy.

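### SAP 3.4 states two incompatible rules for tumor assessments after on-study palliative radiotherapy, so best overall response, and with it the primary ORR, is not uniquely defined

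*SAP*

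**What the plan says.** **Rules that exclude.** The BOR paragraph of SAP 3.4 says, for both RECIST 1.1 and irRC, that "if any alternative antineoplastic therapy is taken while on study, any subsequent assessments will be excluded from the BOR determination". Protocol 14.1.3.1 sets the same default: "If any alternative cancer therapy is taken while on study any subsequent assessments would ordinarily be excluded from the best overall response determination". It adds that if such assessments "are to be included in the main endpoint determination, then this should be described and justified in the protocol". SAP 4.2.3 excludes from irRC BOR anything assessed after new anti-cancer therapy begins, with no exemption.

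**Rule that keeps.** The later SAP 3.4 paragraph on alternative cancer therapy, which covers response-based endpoints under both criteria, says "if any alternative cancer therapy is taken other than palliative radiotherapy any subsequent assessments will be excluded from the analysis of endpoints". Only palliative radiotherapy is exempt.

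**Sensitivity analyses.** If a substantial number of patients (not defined) receive palliative radiotherapy, protocol 10.4.4 says "sensitivity analyses of ORR will be performed where the tumor response assessments are censored at the time of palliative radiotherapy". There, BOR stops at progression or at the "date of subsequent anticancer therapy (including on-treatment palliative radiotherapy of non-target or target lesions". The SAP version, under the same condition, is that "sensitivity analyses of these endpoints may be performed where assessments are also censored at the time of palliative radiotherapy".

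**What radiotherapy is permitted.** Protocol 6.4.3 says "limited-field palliative radiotherapy to non-target lesion(s) may be allowed" in any group. For anaplastic thyroid cancer (ATC) it separately permits limited-field treatment of a life-threatening target lesion, provided other measurable disease remains, and does not call that treatment palliative. These treatments go on an antineoplastic-therapy CRF.

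**The concern.** ORR is the Phase II primary endpoint and is derived from BOR. The BOR paragraph does not name radiotherapy, but the documents place it within anticancer therapy: the CRF title in protocol 6.4.3 does so, protocol 10.4.4 does so expressly, and the SAP needs an exemption only because the general rule would otherwise cover it. Read literally, then, the same scan is dropped by one paragraph and kept by another.

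The decision rules are counts. Preliminary evidence of activity is called at 12 of 60 for NSCLC and 18 of 60 for melanoma (SAP 3.3.2). Protocol 10.8 assumes an efficacy claim in TNBC at an observed ORR of 20%. A single patient can matter when the count is on the boundary.

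A second ambiguity lies in the word palliative, which the SAP does not define. Protocol 6.4.3 attaches it to non-target lesions only; protocol 10.4.4 attaches it to both kinds. If the ATC target-lesion exception counts as palliative, later scans are kept while the irradiated lesion is still in the sum of diameters (protocol Table 14-1). In single-arm Group 4, local shrinkage could then contribute to a partial response (PR) and could not be separated from drug effect.

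**Working it through.** **1. When the rules differ.** Take a patient who meets PR criteria, has non-target palliative radiotherapy before the confirming scan, and meets PR again at least 4 weeks later, before progression. Under the BOR paragraph the second scan is excluded, the PR is unconfirmed and the patient is a non-responder. Under the alternative-therapy paragraph the PR is confirmed and the patient is a responder. The same split arises for irRC between SAP 4.2.3 and the exemption. A response confirmed before radiotherapy is unaffected. For RECIST, only radiotherapy before RECIST progression matters, because BOR stops there.

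**2. Reproducing the plan's figures.** With the Beta(0.25, 1) prior, the posterior is Beta(0.25 + r, 1 + n − r).
- NSCLC, 12/60: Beta(12.25, 49), P(ORR > 15%) = 83.7%, as stated.
- Melanoma, 18/60: Beta(18.25, 43), P(ORR > 20%) = 96.2%, as stated.

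**3. One responder fewer at the boundary.**

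| Group | Count | Observed ORR | Posterior probability |
|---|---|---|---|
| NSCLC, n=60 | 12 → 11 | 20.0% → 18.3% | P(>15%) 83.7% → 74.0% |
| Melanoma, n=60 | 18 → 17 | 30.0% → 28.3% | P(>20%) 96.2% → 93.1% |
| TNBC, n=40 | 8 → 7 | 20.0% → 17.5% | none stated |

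Amendment 08 reports 61 melanoma patients treated. At that size 18/61 = 29.5% already misses 30% and 19/61 = 31.1% meets it, so the boundary is 19 vs 18. TNBC treated 40, as planned. NSCLC treated 118 across two groups and the split is not given, so n = 60 is used.

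If the true ORR equals the reference value, the count falls exactly on the planned-n threshold with binomial probability 12.8% (NSCLC, r=12, p=0.20), 11.2% (melanoma, r=18, p=0.30) and 15.6% (TNBC, r=8, p=0.20). These are not probabilities of a changed call; that also needs an affected responder.

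**4. Group 4, conditional on target-lesion radiotherapy being classed as palliative.**
- PR needs a 30% fall in the sum over all target lesions. With other lesions unchanged, the irradiated lesion's share of the baseline sum times its fractional shrinkage must reach 0.30, so a share below 30% cannot do it alone.
- Illustration with assumed sizes: 60 + 40 = 100 mm becomes 25 + 44 = 69 mm, a 31% fall, although the unirradiated lesion grew.
- With 42 treated, each reclassified patient adds 1/42 = 2.4 points to the observed ORR and 1/43.25 = 2.3 points to the posterior mean.
- The only ATC response data in the documents are 1 confirmed PR in 12 evaluable (Amendment 06 rationale). Scaled: 42 × 1/12 = 3.5 responders, an assumption only.

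| Responders of 42 | P(ORR ≥ 10%) | P(ORR ≥ 20%) |
|---|---|---|
| 3 | 23.4% | 0.8% |
| 4 | 43.0% | 2.7% |
| 5 | 63.0% | 7.0% |

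**The case against.** **The intent is clear.** The exemption is in the paragraph devoted to alternative therapy and covers both response criteria. A sensitivity analysis that censors at palliative radiotherapy would be redundant if the primary analysis already did so. This stands: the natural reading is a general rule with a specific exception. A reader might infer two equally valid primary rules; the documents do not support that. What remains is that two SAP paragraphs and the protocol default contradict the intended rule as written. The derived-variable specifications are in a separate document that is not available here, so which rule was programmed is unknown.

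**Non-target radiotherapy has little power to create responders.** This also stands. Non-target lesions are outside the sum of diameters, and in protocol Table 14-3 a target CR with residual non-target disease is already PR. Irradiating a non-target lesion could at most delay non-target progression. Keeping those scans is defensible; it is simply not written consistently or justified.

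**The Group 4 route is remote.** It needs target-lesion treatment to count as palliative, treatment before RECIST progression, enough share and shrinkage, an investigator PR, and confirmation at least 4 weeks later. Protocol 5.2 bars ATC patients at short-term risk of life-threatening complications, and the Amendment 06 rationale says most early ATC patients progressed or died before the first scan. A reader might infer that Group 4's ORR is inflated; nothing in the documents shows that. Nor can one assume that an investigator's PR always stands: protocol 14.1.4.4 says it is not overruled but also provides for queries and for invalidating a response. The route remains open because protocol 10.4.4 extends the term to target lesions and no rule sets an irradiated lesion aside.

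**Conclusion.** The inconsistency holds and should be fixed. SAP 3.4 (BOR), SAP 4.2.3 and protocol 14.1.3.1 exclude what the SAP 3.4 alternative-therapy paragraph keeps. That paragraph is the intended primary rule, but no justification against the protocol default is given. RECIST and irRC are both affected.

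The size is one responder per affected patient, which is decisive only when a count is on the boundary; the number of affected patients is not given and may be zero. The Group 4 concern is a conditional possibility, worth up to 2.4 points of observed ORR per patient, and not a demonstrated bias. It rests on target-lesion radiotherapy being read as palliative.

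The SAP is also softer than the protocol on the ORR sensitivity analysis (optional rather than required once the condition is met), although it covers more endpoints. Both hang on the undefined substantial number, while a single patient can settle a boundary call.

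**What to change.** These changes concern scoring only; they do not alter which radiotherapy is permitted.

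1. Reconcile both SAP 3.4 paragraphs and SAP 4.2.3 into one rule. For example, state the palliative-radiotherapy exemption in all three, limit it to non-target lesions, and justify it against protocol 14.1.3.1 on the ground that those lesions are not in the sum of diameters.
2. For BOR, ORR and DCR, exclude assessments after radiotherapy to a target lesion unless the response was already confirmed.
3. Match the protocol's firm commitment to the radiotherapy-censored ORR sensitivity analysis. As an addition to the protocol text, run it for any group with an irradiated patient whose BOR differs between the rules, whatever the number.
4. Report irradiated patients by group, and for Group 4 those with target-lesion treatment.
5. Label this a late clarification. Enrollment ended in March 2018 and the SAP is dated July 2020, so show ORR under both readings if primary results were already reported.

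The cost is a SAP amendment or addendum and some matching of irradiated sites to lesions. The documents do not confirm that the radiotherapy CRF identifies the lesion, so medical review or site queries may be needed. ORR could come out slightly lower.

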3.4.1 Phase I: dose-escalation part

Tumor response will be determined per local investigators' assessment, according to RECIST v1.1 and irRC. Response related efficacy assessments will be defined and analyzed based on both RECIST v1.1 and irRC. The endpoints used to evaluate anti-tumor activity are BOR, ORR, DCR, PFS

For all efficacy parameters, data will be listed, summarized, or analyzed by treatment group.

BOR will be summarized. ORR and DCR will be listed and summarized with accompanying 90% exact binomial confidence intervals.

If appropriate, PFS will be presented graphically using Kaplan Meier plots including all patients treated at RP2D/MTD and by treatment group. Median PFS (in months), 25th and 75th percentiles with corresponding 90% CIs and Kaplan-Meier estimated probabilities (PFS rate) with corresponding 90% CIs at 3, 6, 9, and 12 months will be estimated for each treatment group. DOR will be summarized using the mean, minimum and maximum. PFS, along with DOR for patients who experience a CR or PR at any time on study, will be listed by patient.

3.4.2 Phase II part

Tumor response will be determined per local investigators' assessment, according to RECIST v1.1 and irRC. Response related efficacy assessments will be defined and analyzed based on both RECIST v1.1 and irRC. The endpoints used to evaluate anti-tumor activity are BOR, ORR, DCR, DOR, PFS using the FAS.

For all efficacy parameters, data will be listed, summarized, or analyzed by treatment group in Phase II.

BOR will be summarized. ORR and DCR will be summarized and listed with accompanying 90% exact binomial confidence intervals. The waterfall plot of best percent change in the sum of longest diameter (SOD) since baseline with annotation of the BOR for RECIST v1.1 will be provided.

PFS will be listed by patient. PFS (per RECIST v1.1 and irRC) will be presented graphically using Kaplan Meier plots including all patients treated at RP2D/MTD and by treatment in Phase II. Median PFS (in months), 25th and 75th percentiles with corresponding 90% CIs and Kaplan-Meier estimated probabilities (PFS rate) with corresponding 90% CIs at 3, 6, 9, and 12 months will be estimated and summarized for each treatment group. The number (%) of events and subjects censored will also be summarized.

DOR will be listed by patient. If there is a large number of patients achieving response (for example, at least 8 responses in a treatment group), the Kaplan-Meier plots for DOR (per RECIST v1.1 and irRC) will also be produced along with the estimation of the respective medians.

3.5 Safety evaluation

All safety analyses will be based on the Safety Set. The only exceptions will be the summaries of dose limiting toxicities (DLTs) for which the DDS will be used and presented by treatment.

The overall observation period is divided into three mutually exclusive segments:

- 1. pre-treatment period: from day of patient's informed consent to the day before first dose of study treatment
- 2. on-treatment period: from day of first dose of study treatment to 30 days after last dose of study treatment
- 3. post-treatment period: starting at day 31 after last dose of study treatment.

SAP final CSR

Safety summaries will primarily be based on all data from the on-treatment period. Following last administration of PDR001, adverse events (including serious adverse events), and new antineoplastic therapies are collected for a period of 150 days. Following start of new antineoplastic therapy, only study treatment related adverse events will be collected. Select summaries of related adverse events will be produced for the combined on-treatment and posttreatment periods ([CPDR001X2101 Amendment 8 Section 10.5.3.2]).

3.5.1 **Dose-limiting toxicities**

In the Phase I dose-escalation part, DLTs are listed by primary system organ class, worst grade based on the CTCAE version 4.03, and by dose cohort. The Dose determining safety set is used for this summary. By-patient listings will be provided.

